#### ABBREVIATIONS AND DEFINITIONS

AE Adverse event

AESI Adverse events of special interest

ANOVA Analysis of variance AUC Area under curve

AUC0-24h Area under the concentration-time curve of the analyte in plasma over

the time interval from 0 to 24 hours

 $AUC_{\tau,ss}$  Area under the concentration-time curve of the analyte in plasma at

steady state over a uniform dosing interval τ

AUC0-tz Area under the concentration-time curve of the analyte in plasma over

the time interval from 0 to the last quantifiable data point

BA Bioavailability

BI Boehringer Ingelheim

BMI Body mass index (weight divided by height squared)

BP Blood pressure

BPD Borderline personality disorder

CA Competent authority
CI Confidence interval

Cmax Maximum measured concentration of the analyte in plasma

Cmax,ss Maximum measured concentration of the analyte in plasma at steady

state

Cmin Minimum measured concentration of the analyte in plasma

Cmin.ss Minimum measured concentration of the analyte in plasma at steady state

COC Combined oral contraceptive

CRF Case Report Form, paper or electronic (sometimes referred to as 'eCRF')

C-SSRS Colombia-Suicidal Severity Rating Scale

CT Leader
CT Manager
CT Manager
CTP
Clinical Trial Manager
CTP
Clinical trial protocol
CTR
Clinical trial report
CYP
Cytochrome P450
DDI
Drug-drug interaction
DILI
Drug induced liver injury

DRSP Drospirenone
ECG Electrocardiogram

eCRF Electronic case report form

EE Ethinylestradiol

eDC Electronic data capture

Boehringer Ingelheim 19 Oct 2023

BI Trial No.: 1402-0019

c41232811-04 Trial Protocol Page 12 of 84

Proprietary confidential information © 2023 Boehringer Ingelheim International GmbH or one or more of its affiliated companies

EDTA Ethylenediaminetetraacetic acid

EoS End of Study (synonym for End of Trial)

FSH follicle stimulating hormone

GCP Good Clinical Practice

gCV Geometric coefficient of variation

GLP Good Laboratory Practice

gMean Geometric mean

IB Investigator's brochure

ICH International Council for Harmonisation

iCF Intended commercial formulation

ICF Informed Consent Form

IEC Independent Ethics Committee
IPD Important protocol deviation
IRB Institutional Review Board

ISF Investigator site file

LC-MS/MS Liquid chromatography with tandem mass spectrometry

LH Luteinizing hormone

MDA Methylenedioxyamphetamine MDD Major depressive disorder

MDMA Methylenedioxymethamphetamine

MedDRA Medical Dictionary for Regulatory Activities

MRD Multiple-rising dose

NOAEL No observed adverse effect level

PD Pharmacodynamic(s)
PK Pharmacokinetic(s)
PKS Pharmacokinetic set

PR Pulse rate

PTSD Post-traumatic stress disorder

QT interval ECG interval from the start of the QRS complex to the end of the T wave QTc interval QT interval corrected for heart rate, e.g. using the method of Fridericia

(QTcF) or Bazett (QTcB)

R Reference treatment
REP Residual effect period
SAE Serious adverse event

SCR Screening

SmPC Summary of Product Characteristics

SOP Standard operating procedure

ss (at) steady state

c41232811-04

19 Oct 2023

Page 13 of 84

Proprietary confidential information © 2023 Boehringer Ingelheim International GmbH or one or more of its affiliated companies

SUSAR Suspected unexpected serious adverse reaction

**Trial Protocol** 

Test product or treatment Τ

Time from (last) dosing to the maximum measured concentration of the  $t_{max}$ 

analyte in plasma

Time from (last) dosing to the maximum measured concentration of the  $t_{max,ss}$ 

analyte in plasma at steady state

TS Treated set

**TSAP** Trial statistical analysis plan UGT UDP-Glucuronosyltransferase

Upper limit of normal ULN

Apparent volume of distribution during the terminal phase after  $V_z/F$ 

extravascular administration

c41232811-04 Trial Protocol Page 14 of 84

Proprietary confidential information © 2023 Boehringer Ingelheim International GmbH or one or more of its affiliated companies

## 1. INTRODUCTION

is being developed for major depressive disorder (MDD), borderline personality disorder (BPD), and post-traumatic stress disorder (PTSD).

## 1.1 MEDICAL BACKGROUND

MDD is a debilitating disease characterized by low mood and often by low self-esteem, low energy, and a loss of interest. It can strongly impact a person's life and health, including significantly increased risk of suicidality, and is difficult to treat, even with systematic antidepressant strategies. In the National Institute of Mental Health funded STAR\*D trial of >4000 patients with nonpsychotic depression, about 30% of the patients did not reach remission after 4 different medications [P06-11895] and continued to experience residual symptoms [R16-5475] that significantly impacted the patients' quality of life [R06-2872].

BPD is a chronic mental disorder with an estimated prevalence of around 2% in the general community [R16-5476] and severely impaired quality of life [R16-5474]. The main symptom clusters of BPD include impulsive-behavioural dyscontrol, cognitive-perceptual symptoms, disturbed interpersonal relations, and affective instability. Patients with BPD have high rates of deliberate self-harm and a rate of completed suicide that is 50 times higher than in the general population [R16-5477]. Even the presence of a single diagnostic feature of BPD is predictive for poor functioning and psychiatric illness burden [R16-5483]. Treatment guidelines recommend psychotherapy as the mainstay of treatment, but pharmacotherapy is commonly used as an adjunctive, symptom-targeted component of treatment. However, no drug is approved for the treatment of BPD.

PTSD is a disabling mental disorder that can develop after first- or second-hand exposure to a traumatic event. Lifetime prevalence in the US was estimated at 6.8%, with 1-year prevalence at 3.6%, but more than twice as high in women (5.2%) than men (1.8%) [R08-4516]. Classic symptoms involve intrusive flashbacks and nightmares of the trauma [R15-4424]. The firstline treatment in adults is psychotherapy, such as cognitive behavioural therapy. Only sertraline and paroxetine (both antidepressants of the serotonin reuptake inhibitor class) have been licensed for the treatment of PTSD in the US, EU, Japan and several other regions globally [R21-1276].

BI Trial No.: 1402-0019

[figure not shown]
c41232811-04 Trial Protocol

Page 15 of 84

Proprietary confidential information © 2023 Boehringer Ingelheim International GmbH or one or more of its affiliated companies

## 1.2 DRUG PROFILE

## 1.2.1 BI1358894

c41232811-04 Trial Protocol

Protocol Page 16 of 84

Proprietary confidential information © 2023 Boehringer Ingelheim International GmbH or one or more of its affiliated companies

## Clinical pharmacology

At the time of last IB update (July 2023), 312 healthy volunteers and 73 patients with MDD had participated in 12 completed Phase I clinical trials with BI 1358894. In Phase II, there have been 2 completed trials, which included 45 patients with MDD and 390 patients with BPD[c10354149].

For a more detailed description of the BI 1358894 profile, please refer to the current Investigator's Brochure (IB) [c10354149].

Proprietary confidential information © 2023 Boehringer Ingelheim International GmbH or one or more of its affiliated companies

## 1.2.2 Yasmin® (ethinylestradiol + drospirenone)

## 1.2.2.1 Ethinylestradiol

Ethinylestradiol (EE) is a synthetic estrogen with actions similar to those of estradiol. It is frequently used as the estrogenic component of combined oral contraceptives; a typical daily dose is 20 to 40 µg. Ethinylestradiol has also been used for hormone replacement therapy. Ethinylestradiol is also used for the treatment of female hypogonadism and the palliative treatment of prostate cancer and malignant breast cancer.

The adverse effects of EE and other estrogens are related, in part, to dose and duration of therapy, and to the sex and age of the recipient. In addition, adverse effects may be modified by administration of progestogen in combined oral contraceptives or hormone replacement therapy. Whether adverse effects of natural and synthetic estrogens differ, and whether the route of administration has an effect, is less clear. The use of estrogens in girls may cause premature closure of the epiphyses resulting in decreased final adult height. Large doses of estrogens used in palliative care have also been associated with nausea, fluid retention, venous and arterial thrombosis, and cholestatic jaundice. In men, large doses of estrogen cause impotence and feminising effects such as gynaecomastia. In women, uterine bleeding may occur after the cessation of estrogen therapy.

Ethinylestradiol is rapidly and well absorbed from the gastrointestinal tract with maximum plasma concentrations occurring after 1 h. The presence of an ethinyl group at the 17-position greatly reduces hepatic first-pass metabolism compared with estradiol, enabling the compound to be much more active after oral dosing, but there is some initial conjugation by the gut wall and systemic bioavailability is only about 45% (20-65%). Ethinylestradiol is highly protein bound (98%), but unlike naturally occurring estrogens which are mainly bound to sex-hormone binding globulin, it is principally bound to albumin. The apparent volume of distribution is 2.8 to 8.6 L/kg. It is metabolised in the liver by hydroxylation (mediated by CYP3A4) followed by glucuronidation (UGT1A1) and sulfatation of metabolites that undergo enterohepatic recycling. Metabolites are excreted via urine (40%) and bile (60%). The terminal half-life of ethinylestradiol is 10 to 20 h [R13-3708].

For a more detailed description of ethinylestradiol, please refer to the SmPC of Yasmin® [R23-0484].

## 1.2.2.2 Drospirenone

Drospirenone (DRSP) is a synthetic progestin used in oral contraceptives for the prevention of pregnancy. It is commonly found in combination with EE in combined oral contraceptives (COC). Aside from its contraceptive effects, DRSP is used with estrogens to control acne and premenstrual dysphoric disorder. DRSP and EE in combination inhibit the release of follicle stimulating hormone (FSH) and luteinizing hormone (LH), resulting in ovulation suppression. Other changes include changes in the cervical mucus consistency, hindering sperm movement and preventing embryo implantation. DRSP is an analog of the diuretic spironolactone, which means that DRSP has ant mineralocorticoid activity. Therefore, DRSP should not be used in patients with renal or hepatic impairment or adrenal insufficiency. Progesterone and the progestogens may cause gastrointestinal disturbances, changes in appetite or weight, fluid

c41232811-04 Trial Protocol Page 18 of 84

Proprietary confidential information © 2023 Boehringer Ingelheim International GmbH or one or more of its affiliated companies

retention, oedema, acne, chloasma (melasma), allergic skin rashes, urticaria, mental depression, breast changes including discomfort or occasionally gynaecomastia, changes in libido, hair loss, hirsutism, fatigue, drowsiness or insomnia, fever, headache, premenstrual syndrome-like symptoms, and altered menstrual cycles or irregular menstrual bleeding. Anaphylaxis or anaphylactoid reactions may occur rarely (<0.01%).

After an oral dose DRSP is rapidly absorbed, with a bioavailability of about 76% due to first-pass effect. It is about 97% bound to plasma proteins, likely to albumin. The maximum concentration occurs within 1 to 2 hours. It is heavily metabolized with a terminal half-life of about 30 to 40 hours. DRSP undergoes oxidative metabolism via the hepatic cytochrome enzyme CYP3A4. The metabolites are excreted in urine and faeces. [R23-0688].

For a more detailed description of drospirenone, please refer to the SmPC of Yasmin® [R23-0484].

## 1.2.2.3 Safety

Combined oral contraceptives (COC) including Yasmin® should not be used in the following conditions. Should any of the conditions appear for the first time during COC use, the product should be stopped immediately.

- Presence or risk of venous thromboembolism (VTE)
- Presence or risk of arterial thromboembolism (ATE)
- Presence or history of severe hepatic disease or liver tumors
- Current or history of breast cancer
- Hypersensitivity to the active substances or to any of the excipients

The frequency of diagnosis of breast cancer is very slightly increased among COC users. As breast cancer is rare in women under 40 years of age the excess number is small in relation to the overall risk of breast cancer. Causation with COC use is unknown.

The most common adverse events with Yasmin® are nausea, headache, migraine, depressed mood, menstrual cycle alteration, breast tenderness, vaginal discharge and candidiasis vulvovaginal altered mood, breast pain, and breast tenderness.

Less common adverse events are changes in the libido, hypertension, hypotension, vomiting, diarrhoea, acne, eczema, pruritus, alopecia, breast hypertrophy, vaginal infections, fluid retention and weight changes.

Rare adverse events are hypersensitive reactions, asthma, hearing loss, venous and arterial thromboembolism, erythema nodosum, erythema multiforme and discharge of the mammary glands.

Drospirenone, as many other progestogens, has been linked to increased risk of venous thromboembolism [R23-0501] A statement from FDA concluded that the increase in the risk of thromboembolism resulting from the use of drospirenone remains unclear; in its statement, the FDA mentioned that increased risk of venous thromboembolism with oral contraceptives such as drospirenone exists but remains lower than the risk of this condition during pregnancy and during the postpartum period [R23-0680].

c41232811-04 Trial Protocol

Page 19 of 84

Proprietary confidential information © 2023 Boehringer Ingelheim International GmbH or one or more of its affiliated companies

For a complete listing of adverse reactions including frequency of occurrence please refer to the current version of the summary of product characteristics (SmPC) [R23-0484].

#### 1.2.3 Residual Effect Period

The REP of ethinylestradiol is 5 days based on a minimum observation period of at least 5-fold estimated  $t\frac{1}{2}$  (i.e. 5 x 20 h, or 4.2 days, rounded to 5 days). The REP of drospirenone is 6 days based on a minimum observation period of at least 5-fold estimated  $t\frac{1}{2}$  (i.e. 5 x 40 h, or 8.3 days, rounded up to 9 days).

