c41232811-04 Trial Protocol Page 6 of 84

Period	Visit	Day	Planned time (relative to first drug administration) [h:min]	Approximate clock time of actual day [h:min]	Event and comment	Safety laboratory	PK plasma, BI 1358894	PK plasma, COC	Exploratory PD serum 	12-lead ECG	Vital signs (BP, PR)	Suicidality Assesssment 	Questioning for AEs and concomitant therapy 
			486:00	14:00				X					X
			488:00	16:00	Snack (voluntary) 			X					X
			490:00	18:00				X					X
			492:00	20:00	Dinner 			X					X
		22	504:00	08:00	Breakfast  , discharge from trial			X		X	X	X	X
					site								
		23-28			Follow-up call (COC free							X	X
					interval)								
EoS	5	42 to 52			End of study (EoS) examination 	C 				X	X	X	X

- Subject must be informed and written informed consent obtained prior to starting any screening procedures. Screening
  procedures include physical examination, check of vital signs, ECG, safety laboratory (including drug screening and
  cotinine test), demographics (including determination of body height and weight, smoking status and alcohol history),
  relevant medical history, concomitant therapy and review of inclusion/exclusion criteria. In addition, a gynaecological
  examination will be performed prior to trial entry.
- 2. Pre-dose
- 3. If several actions are indicated at the same time, the intake of meals will be the last action.
- 4. At the end of study (synonym for end of trial), the EoS examination includes physical examination, body weight, vital signs, ECG, safety laboratory, recording of AEs and concomitant therapies.
- 5. AEs and concomitant therapies will be recorded throughout the trial, but will be specifically asked for at the times indicated in the Flow Chart above.
- 6. Including hematology, biochemistry, coagulation, urinalysis, drug screen (only at screening), cotinine test (only at screening) and serum pregnancy test.

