## 3.3.4 Withdrawal of subjects from treatment or assessments

Subjects may withdraw or may be removed from trial treatment or may withdraw consent to trial participation as a whole ('withdrawal of consent') with very different implications; please see Section 3.3.4.1 and 3.3.4.2 below.

If a subject is removed from or withdraws from the trial prior to the first administration of trial medication, the data of this subject will not be entered in the case report form (CRF) and will not be reported in the clinical trial report (CTR).

c41232811-04 Trial Protocol Page 33 of 84

19 Oct 2023

Proprietary confidential information © 2023 Boehringer Ingelheim International GmbH or one or more of its affiliated companies

If a subject is removed from or withdraws from the trial after the first administration of trial medication, this will be documented and the reason for discontinuation must be recorded in the CRF; in addition, trial data will be included in the CRF and will be reported in the CTR.

Following removal or withdrawal, a complete end-of-trial examination should be performed. If the discontinuation or withdrawal occurs before the end of the REP (see Section 1.2.3), the discontinued subject should, if possible, be questioned for AEs and concomitant therapies at or after the end of the REP, in order to ensure collection of AEs and concomitant therapies throughout the REP, if not contrary to any consent withdrawal of the subject.

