#### 5.2.6.2 Adverse event collection and reporting

#### 5.2.6.2.1 AE collection

Upon enrolment into a trial, the subject's baseline condition is assessed (for instance, by documentation of medical history/concomitant diagnoses), and relevant changes from baseline are noted subsequently.

Subjects will be required to report spontaneously any AEs. In addition, each subject will be regularly assessed by the medical staff throughout the clinical trial and whenever the investigator deems necessary. As a minimum, subjects will be questioned for AEs (and concomitant therapies) at the time points indicated in the Flow Chart. Assessment will be made using non-specific questions such as 'How do you feel?'. Specific questions will be asked wherever necessary in order to more precisely describe an AE.

A carefully written record of all AEs shall be kept by the investigator in charge of the trial. Records of AEs shall include data on the time of onset, end time, intensity of the event, and any treatment or action required for the event and its outcome.

The following must be collected and documented on the appropriate CRF(s) by the investigator:

- From signing the informed consent onwards until an individual subject's end of trial (the End of Study (EoS) visit):
  - o All AEs (serious and non-serious) and all AESIs
  - The only exception to this rule are AEs (serious and non-serious) and AESIs in Phase I trials in healthy volunteers, when subjects discontinue from the trial due to screening failures prior to administration of any trial medication. In these cases, the subjects' data must be collected at trial site but will not be entered in the CRF and will not be reported in the CTR.

BI Trial No.: 1402-0019

c41232811-04 Trial Protocol Page 51 of 84

Proprietary confidential information © 2023 Boehringer Ingelheim International GmbH or one or more of its affiliated companies

• After the individual subject's end of trial:

o The investigator does not need to actively monitor the subject for new AEs but should only report any occurrence of cancer and trial treatment related SAEs and trial treatment related AESIs of which the investigator may become aware of by any means of communication, e.g. phone call. Those AEs should be reported on the BI SAE form (see Section 5.2.6.2.2), but not on the CRF.

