#### 6. INVESTIGATIONAL PLAN

#### 6.1 VISIT SCHEDULE

Exact times of measurements outside the permitted time windows will be documented. The acceptable time windows for screening and the end of trial examination are provided in the Flow Chart.

Study measurements and assessments scheduled to occur 'before' trial medication administration are to be performed and completed within a 2 h-period prior to the trial drug administration.

If not stated otherwise in the Flow Chart, the acceptable deviation from the scheduled time for vital signs, ECG, and laboratory tests will be  $\pm$  30 min.

If scheduled in the Flow Chart at the same time as a meal, blood sampling, vital signs, and 12-lead ECG recordings have to be done first. Furthermore, if several measurements including venipuncture are scheduled for the same time, venipuncture should be the last of the measurements due to its inconvenience to the subject and possible influence on physiological parameters.

For planned blood sampling times, refer to the Flow Chart. While these nominal times should be adhered to as closely as possible, the actual sampling times will be recorded and used for the determination of pharmacokinetic parameters.

During the run-in period, administration of Yasmin® tablets must be done by the subjects at home. The subjects are advised to take Yasmin® tablets with a cup of water at the same time each day, approximately between 06.00 and 10.00 am local time.

Ambulatory dosing in periods 1 and 2 should be performed between 06.00 and 10.00 am local time.

If a subject misses an ambulatory visit in weeks 1 or 2 of any period all efforts should be made for the subject to attend the visit as soon as possible. In such case dosing of Yasmin® can occur at any time of the day or can even be taken together with the next planned dose.

. If a subject misses 2 visits they must be separated by at least 7 days. Subjects who miss a visit in weeks 1 or 2 will be reminded of the importance of using additional contraception methods. All visits in week 3 must be attended. The relevance of measurements outside the permitted time windows will be assessed no later than at the Report Planning Meeting.

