### 7.2.5 Safety analyses

Safety will be analysed based on the assessments described in Section 2.2.2.3. All treated subjects (TS, refer to Section 7.2) will be included in the safety analysis. Safety analyses will be descriptive in nature and based on BI standards. No hypothesis testing is planned.

Boehringer Ingelheim BI Trial No.: 1402-0019

c41232811-04 Trial Protocol Page 61 of 84

19 Oct 2023

Proprietary confidential information © 2023 Boehringer Ingelheim International GmbH or one or more of its affiliated companies

For all analyses, the treatment actually administered (= treatment at onset) to the subject will be used (any deviations from the assigned treatment will be discussed in the minutes of the Report Planning Meeting).

Treatments will be compared in a descriptive way. Tabulations of frequencies/proportions will be used to evaluate categorical (qualitative) data, and tabulations of descriptive statistics will be used to analyse continuous (quantitative) data.

Measurements (such as ECG, vital signs, or laboratory parameters) or AEs will be assigned to treatments (see Section 4.1) based on the actual treatment at the time of the measurement or on the recorded time of AE onset (concept of treatment emergent AEs). Therefore, measurements performed or AEs recorded prior to first intake of trial medication will be assigned to the screening period. Those occurring in the run-in period will be assigned to the run-in period, while all others -from first trial medication intake in respective treatment period to end of REP (see Section 1.2.3) will be assigned to the respective treatment period. Events occurring after the REP but prior to end of study examination date will be assigned to follow-up'. In case of two or more treatments, the follow-up will be summarized according to the previous treatment. These assignments including the corresponding time intervals will be defined in detail in the TSAP. Note that AEs occurring after the last per protocol contact but entered before final database lock will be reported to Pharmacovigilance only and will not be captured in the trial database.

Additionally, further treatment intervals (analysing treatments) may be defined in the TSAP in order to provide summary statistics for time intervals, such as combined treatments, ontreatment totals, or periods without treatment effects (such as screening and follow-up intervals).

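### Does the 6-day residual effect period printed for drospirenone in protocol Section 1.2.3 need correcting, when its own calculation and the SAP give 9 days?

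*Protocol*

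**What the plan says.** Protocol Section 1.2.3 sets the residual effect period (REP) by one rule, at least five half-lives. For ethinylestradiol it takes 20 h, obtains 4.2 days and states 5. For drospirenone it says "The REP of drospirenone is 6 days based on a minimum observation period of at least 5-fold estimated" half-life, and the bracket in the same sentence gives 5 x 40 h, "or 8.3 days, rounded up to 9 days". Section 1.2.2.2 describes drospirenone as having a "terminal half-life of about 30 to 40 hours".

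The protocol uses the REP in two places:

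- Section 3.3.4, for subjects who stop before the REP has ended: "the discontinued subject should, if possible, be questioned for AEs and concomitant therapies at or after the end of the REP".
- Section 7.2.5, which assigns events "from first trial medication intake in respective treatment period to end of REP (see Section 1.2.3") to that treatment period. The same sentence first assigns events in the run-in to the run-in, and the paragraph leaves the detailed intervals to the SAP.

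Collection does not depend on the REP. Section 5.2.6.2.1 runs it "From signing the informed consent onwards until an individual" subject's end-of-study visit. Section 6.1 notes that "The acceptable time windows for screening and the end of trial examination are provided in the" Flow Chart, which puts the "End of study (EoS) examination" on Day 42 to 52.

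SAP Section 6.1 repeats protocol Section 1.2.3 with 9 days where the protocol has 6. It also gives 17 days for BI 1358894, and overall for adverse events. Because nobody received BI 1358894, it then applies 9 days: the on-treatment phase ends 216 h after the last contraceptive dose or at trial termination, whichever is first. SAP Section 4 records that no subject started Period 1, and Section 6.1 that 28 were treated in the run-in.

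**The concern.** A single sentence gives two values for a quantity that bounds the adverse event window. The SAP then reproduces the sentence as protocol text with the other value. Neither its list of changes (Section 4) nor its history table mentions the difference, and no protocol amendment describes a change to Section 1.2.3.

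The drospirenone figure is the longer of the two contraceptive REPs, so it sets the window for subjects exposed to the contraceptive alone, which is everyone treated. Under SAP Section 6.1, CTR Section 15.3 and the ClinicalTrials.gov appendix show the on-treatment phase only. An event starting between 144 h and 216 h after the last dose is therefore in those tables under 9 days and outside them under 6. A withdrawn subject could also be questioned three days sooner under the shorter figure.

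**Working it through.** **Inputs.** Half-lives of 20 h (ethinylestradiol) and 40 h (drospirenone) and the five-fold rule, from protocol Section 1.2.3; the 30 to 40 h range from Section 1.2.2.2; 216 h and 17 days from SAP Section 6.1.

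**Formula.** REP in days = 5 x half-life / 24, rounded up.

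| Case | 5 x half-life | Days | Rounded up | Printed in protocol |
|---|---|---|---|---|
| Ethinylestradiol, 20 h | 100 h | 4.17 | 5 | 5 |
| Drospirenone, 40 h | 200 h | 8.33 | 9 | 6, then 9 |
| Drospirenone, 30 h | 150 h | 6.25 | 7 | not used |

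The rule reproduces the ethinylestradiol figure and the 9 in the drospirenone bracket, but not the 6. Six days would satisfy the rule only for a half-life of at most 144 / 5 = 28.8 h, below the protocol's own range. At 40 h, 6 days covers 144 / 40 = 3.6 half-lives and 9 days covers 216 / 40 = 5.4. The shortfall against the rule is 200 - 144 = 56 h (28%), and the two printed figures differ by 216 - 144 = 72 h. No reading of the sentence's own inputs gives 6, which points to a slip rather than a second rule.

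**Where the 72 h could act.**

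1. *The 28 run-in subjects, analysis.* Section 7.2.5 assigns run-in events to the run-in; its REP boundary is written for the treatment periods, which nobody entered. The window used is the SAP's, stated in hours (216 h) and free of ambiguity.
2. *Withdrawn subjects, Section 3.3.4.* The request is qualified by feasibility and has no upper time limit. A contact at 9 days meets it under either figure, and collection runs to the end-of-study visit regardless.
3. *Completers, had there been any.* From the Day 21 dose to the earliest end-of-study day is 42 - 21 = 21 days = 504 h, beyond 144 h, 216 h and 17 days (408 h).
4. *Between Periods 1 and 2, had there been any.* Periods last 28 days, so the next first dose comes 28 + 1 - 21 = 8 days = 192 h after the Day 21 dose. A literal 6 days would have labelled 192 - 144 = 48 h as follow-up; 9 or 17 days would have left no such interval. No subject reached this point.

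**The case for a change.** The best case for acting is that the number is operative. With nobody exposed to BI 1358894, the SAP sets the 17-day period aside, so the drospirenone REP fixes the on-treatment phase for every treated subject and decides which events enter the main tables. The end-of-study timing that protects completers does not help, because there were none. The SAP also altered a digit inside text that it presents as the protocol's, and one sentence of disclosure would cost almost nothing.

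Most of the facts stand: the contradiction, the arithmetic, the silent substitution, and the link between the window and the tables. What does not follow is a change to the plan. The protocol hands the exact intervals to the SAP, and the SAP adopts the value that the protocol itself calculates. Section 4 of the SAP is for changes to the planned analysis, and using the protocol's derived figure is not one. The SAP's protocol extracts are not strictly verbatim elsewhere either: the note on late adverse events in Section 7.2.5 loses a word in SAP Section 6.1. Disclosure would improve the record without altering any table.

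**Conclusion.** The slip is genuine as printed, but it is clerical and its correction brings no gain to the analysis. The calculation beside the 6 and SAP Section 6.1 both give 9 days, and the planned on-treatment phase already uses 216 h. The size is 72 h on paper and zero in planned results: no pharmacokinetic analysis, sample-size figure or planned adverse event table depends on the 6. The one protocol use that could be affected is the earliest time for questioning subjects who withdraw, and their events are collected to the end-of-study visit anyway. The trial has stopped, so no future subject depends on it. If the protocol is ever reissued, the two figures in Section 1.2.3 should be reconciled.

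This rests on three points. The public text shows the true digit, which should be checked in the PDF: protocol Section 3.1 has plus-minus signs where the SAP's extract of that section has plus signs, so a misread character is possible. The number of events with onset between 144 h and 216 h is not given and may be zero, but the SAP's rule for placing them is explicit. The 17-day period in the SAP may come from redacted protocol text; if it governs overall, the 6-day figure would have set no window even in the full trial.
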